10 SAFETY ANALYSES

All analysis of safety variables will be performed using the SS, MS, and AMS.

The AMS will be used for summaries of safety that include data from the Initial Treatment Period and Maintenance Treatment Period.

Summaries of safety will be presented for the Initial Treatment Period, Maintenance Treatment Period, and combined Initial and Maintenance Treatment Period unless specified otherwise.

10.1 Extent of exposure

Summaries for exposure will be provided. This consists of a descriptive summary of study medication duration in days. In addition, total study medication duration and time at risk will be summarized in years by treatment group and treatment period (ie, the Initial Treatment Period, the Maintenance Treatment Period, and the Initial and Maintenance Treatment Period). Summary of exposure in Maintenance Treatment Period will be on MS. The cumulative study medication duration will be summarized for study participants exposed for given durations of time. For the cumulative duration through Week 48 the following categories for duration will be used:

- >0 weeks
- ≥ 4 weeks
- ≥ 8 weeks
- ≥ 12 weeks
- ≥ 16 weeks
- ≥ 20 weeks
- ≥ 24 weeks
- ≥ 28 weeks
- ≥ 32 weeks
- ≥ 40 weeks
- ≥ 48 weeks

Definitions for study medication duration and time at risk in days are provided below for each period. Time at risk will be summarized in years. Time at risk in years is calculated by dividing the time at risk in days by 365.25.

Throughout this section, date of last clinical contact for each participant is defined as the maximum of (last visit date including SFU visit, last imputed AE start date, date of study termination or completion, last date of study drug administration).

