Per protocol, visit windows are ± 3 days from the date of first dose. The 20-week SFU Visit window is ± 7 days from the date of the final dose. All-by-visit summaries will contain nominal (ie, scheduled) visits only. Unscheduled visits will not be mapped to scheduled visits except for assessments that occur within a 3-day time window of a scheduled visit. In that case, the assessment will be mapped to the corresponding scheduled visit and will be used for the analysis. This will only occur for selected vendor data. The only exception to this rule is for unscheduled assessments that occur up to 3 days after the Baseline visit. These unscheduled visits will remain as unscheduled as the Baseline assessment cannot be after the first dose of study drug administration. See Section 3.3 for more details on the definition of Baseline values.

A complete set of data listings containing all documented data as well as calculated data (eg, change from Baseline) will be generated.

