10.1.1.1 Study medication duration (days)

Definitions for study medication duration (days) are provided as follows:

- Date of last dose in the Initial Treatment Period – Date of first dose in the Initial Period + 14 days.

Note: The use of 14 days assumes a Q2W dosing interval (bimekizumab 320mg Q2W and placebo). For participants randomized to bimekizumab 320mg Q4W, this will be adjusted based on the dosing interval (eg, use Date of last bimekizumab dose in the Initial Treatment Period – Date of first dose in the Initial Period + 28 days).

Note: If date of last dose in the Initial Treatment Period + 14 days (or + 28 days in the case of Q4W dosing) extends to a date beyond the date of first dose in the Maintenance Treatment Period, then this calculation reverts to:

- Date of first dose in the Maintenance Treatment Period – Date of first dose in the Initial Treatment Period + 1.
- For participants who die during the Initial Period, if date of last dose in the Initial Period + 14 days (or date of last bimekizumab dose in the Initial Treatment Period + 28 days in the case of Q4W dosing) extends to a date beyond the date of death, then this calculation reverts to:
 - Date of death – Date of first dose in the Initial Period + 1.

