10.1.2.1 Study medication duration (days)

Definitions for study medication duration (days) are provided as follows:

- Date of last dose in the Maintenance Treatment Period – date of first dose in the Maintenance Treatment Period + 14 days.

The use of 14 days assumes a Q2W dosing interval. For participants randomized to bimekizumab 320mg Q4W in the Maintenance Treatment Period, this will be adjusted based on the dosing interval (eg, use Date of last bimekizumab dose in the Maintenance Treatment Period – date of first dose in the Maintenance Treatment Period + 28 days).

Note: If date of last dose in the Maintenance Treatment Period + 14 days (or + 28 days in the case of Q4W dosing) extends to a date beyond the final visit date of the Maintenance Treatment Period (not including SFU), then this calculation reverts to:

- Final visit date of the Maintenance Treatment Period (not including SFU) – date of first dose in the Maintenance Treatment Period + 1.
- For participants who die during the Maintenance Treatment Period, then this calculation reverts to:
 - Date of death – Date of first dose in the Maintenance Treatment Period + 1.

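### The ≥ 48 weeks exposure row leaves no room for the ±3-day visit window, and the Maintenance death rule can credit exposure after drug was stopped

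*SAP*

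**What the plan says.** SAP section 10.1 works in days: "This consists of a descriptive summary of study medication duration in days". It then states: "The cumulative study medication duration will be summarized for study participants exposed for given durations of time", and adds: "For the cumulative duration through Week 48 the following categories for duration will be used". The rows run from > 0 to ≥ 48 weeks, and the last three are ≥ 32, ≥ 40 and ≥ 48 weeks. No tolerance and no day-to-week conversion are given.

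- **Initial Period (10.1.1.1, Q2W and placebo):** "Date of last dose in the Initial Treatment Period – Date of first dose in the Initial Period + 14 days". If that end date passes the first Maintenance dose, the duration becomes "Date of first dose in the Maintenance Treatment Period – Date of first dose in the Initial Treatment Period + 1".
- **Maintenance Period (10.1.2.1):** last dose minus first Maintenance dose, plus 14 days. If the end date "extends to a date beyond the final visit date of the Maintenance Treatment Period (not including SFU), then this calculation reverts to" final visit minus first Maintenance dose, plus 1.
- **Combined (10.1.3.1):** the sum of the two, less 1 day where the Initial cap applied.
- **Q4W:** 28 days replace 14.
- **Visit timing (3.1):** "visit windows are ± 3 days from the date of first dose".
- **Deaths:** 10.1.1.1 cuts the duration at death only when last dose plus the dosing interval would run past the date of death. Section 10.1.2.1 says only: "For participants who die during the Maintenance Treatment Period, then this calculation reverts to" date of death minus first Maintenance dose, plus 1.

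**The concern.** The ≥ 48 weeks row is the one a reader will take as the number exposed for the whole treatment period. Its cut-point equals the value that a perfectly timed participant reaches, so a dose one day early can remove a full completer. The next row down is ≥ 40 weeks, so that person is shown alongside someone who stopped about 8 weeks early. Part of the error runs in one direction only: a late Week 16 dose costs days, and an early one never gains any.

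The death rule is a separate matter. Read literally, it counts time off drug as time on drug for anyone who stopped treatment, stayed in the study and later died during Maintenance.

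**Working it through.** **Inputs.** Injections are every 2 weeks from Week 0 to Week 46 (section 7), so the last doses are Week 14 (Day 98 after first dose) and Week 46 (Day 322). The nominal Week 16 dose is Day 112 and the final visit is Day 336. The window is ±3 days (3.1). That 48 weeks means 48 × 7 = 336 days is an inference.

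**On schedule.** Initial: 98 + 14 = 112 days, which matches the 112-day period length in 10.1.1.2. Maintenance: 322 − 112 + 14 = 224. Combined: 112 + 224 = 336 days, exactly at the cut-point.

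**General formula.** Let e14, e16, e46 and e48 be the offsets in days of those four visits.

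- Initial, after the 1-day correction in 10.1.3.1: 112 + min(e14, e16)
- Maintenance: 224 − e16 + min(e46, e48 + 1)
- Combined: 336 + min(0, e14 − e16) + min(e46, e48 + 1)

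**Single departures.** Week 14 dose one day early: 335. Week 16 dose one day late: 335. Week 46 dose one day early: 335. Final visit one day early: still 336, because of the + 1 in the cap; two days early: 335. All four visits three days late: 339. The in-window minimum is 336 − 6 − 3 = 327.

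**Example.** Doses on Days 0, 98, 115 and 322 (among others) and final visit on Day 336: 112 + (322 − 115 + 14) = 112 + 221 = 333 days. No dose was missed, but the participant is counted only as ≥ 40 weeks.

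**Share below 336 days, independent uniform ±3-day offsets.** Write A = min(0, e14 − e16) and B = min(e46, e48 + 1).

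- P(A = 0) = 28/49; P(A = −1, −2, −3) = 6/49, 5/49, 4/49
- P(B ≥ 0, 1, 2, 3) = 20/49, 12/49, 6/49, 2/49
- P(A + B ≥ 0) = (28×20 + 6×12 + 5×6 + 4×2)/2401 = 670/2401 = 27.9%, so 72.1% fall below

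The same enumeration under other timing assumptions gives:

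| Assumed timing of full completers | Below 336 days |
|---|---|
| 90% of visits on the exact day, rest spread evenly over ±3 | 16.7% |
| 80% on the exact day | 30.3% |
| 70% on the exact day | 41.3% |
| Weeks 14/16 share one shift and Weeks 46/48 another, uniform ±3 | 42.9% |
| 60% on the exact day | 50.0% |
| Independent uniform ±1 | 50.6% |
| Independent uniform ±2 | 66.4% |
| Independent uniform ±3 | 72.1% |

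**Q4W.** These figures carry over if the caps use the last bimekizumab dose (Weeks 12 and 44, + 28). The cap notes say only last dose. If that means the last injection of any kind, last dose + 28 always passes the period end. For Q4W throughout, the combined duration is then 337 + e48, and only 2/7 = 28.6% fall below under uniform ±3.

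**Effect on average duration.** Under uniform ±3 the dropped gap averages (1×6 + 2×5 + 3×4 + 4×3 + 5×2 + 6×1)/49 = 56/49, about 1.1 days per person.

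**Death rule.** As written, minus the duration to last dose + 14: (death − first Maintenance dose + 1) − (last dose − first Maintenance dose + 14) = (death − last dose) − 13 days. With 28 days for Q4W, the excess is the days since the last bimekizumab dose minus 27.

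**The case against.** A reader might infer that most full completers will miss the top row. The documents do not support that. The SAP gives the width of the window and nothing about how visits fall inside it. Where the off-day visits are spread over ±3 days, the majority is lost once about 60% of visits fall on the exact day; it is also lost if neighbouring visits move together.

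A reader might also suspect the ≥ 16 weeks row. The listed categories belong to cumulative duration through Week 48, and no in-window completer falls below 327 days, so that row misclassifies no full completer.

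It can further be said that a strict cut-off is accurate, that counting coverage only to last dose plus interval is defensible, and that calling 327 days ≥ 48 weeks would mislabel the row. The labelling point stands, and the strict row should stay. The coverage argument is weaker. The SAP's own time-at-risk rules run straight through the Week 14–16 gap (to the first Maintenance dose in 10.1.1.2, and from first dose to final visit in 10.1.3.2 for those entering the extension), yet the drug-duration rule drops those days for someone who never stopped.

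Finally, this is descriptive output. Time at risk is defined separately, the exposure-adjusted rates (EAIR and EAER) rest on it, and no test uses the row. That is correct and limits the weight of the point. The missing death condition looks like a drafting slip, but a programmer following the text would implement it.

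**Conclusion.** The point holds in a limited form. The ≥ 48 weeks row has zero slack, and ordinary in-window timing moves a substantial share of full completers to ≥ 40 weeks: about 17% to 72% across the assumptions tried. The range rests on assumed timing, on 48 weeks meaning 336 days, and, for Q4W, on the caps using the last bimekizumab dose. The dropped Week 14–16 gap is an error in one direction, small on average, but it matters at a cut-point set exactly on the nominal value.

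The death rule in 10.1.2.1 is wrong as written whatever the visit timing. It will affect only participants who stopped drug and later died during Maintenance. Neither problem reaches time at risk, EAIR, EAER or any efficacy or safety comparison.

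**What to change.** 1. **Death rule, 10.1.2.1.** Add the condition that the date of last dose + 14 days (or last bimekizumab dose + 28 days for Q4W) falls after the date of death, as in 10.1.1.1.
2. **Combined duration, 10.1.3.1.** For participants who continue into Maintenance, compute from first dose to the earlier of last dose plus dosing interval and the final visit, without dropping the Week 14–16 gap.
3. **Top row, 10.1.** Keep the strict ≥ 48 weeks row and add a clearly labelled full-period row. Define it by receipt of the scheduled Week 46 injection plus the Week 48 visit, or by a stated visit-window tolerance. Item 2 alone is not enough: without the + 1 at the final visit, 1 − (4/7)² = 33/49, about 67%, would still be below 336 days under uniform ±3. A tolerance must match the revised formula, whose in-window minimum is 336 − 3 = 333 days, not the present 327.
4. **Q4W caps, 10.1.1.1, 10.1.2.1 and 10.1.3.1.** State whether they use the last bimekizumab dose or the last injection, whichever is intended.

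The cost is SAP wording, one revised derivation and one extra table row. No new data are needed.

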10.1.1 Exposure during the Initial Treatment Period

Definitions for study medication duration (days) and time at risk (days) during the Initial Treatment Period are provided as follows:

10.1.1.1 Study medication duration (days)

Definitions for study medication duration (days) are provided as follows:

- Date of last dose in the Initial Treatment Period – Date of first dose in the Initial Period + 14 days.

Note: The use of 14 days assumes a Q2W dosing interval (bimekizumab 320mg Q2W and placebo). For participants randomized to bimekizumab 320mg Q4W, this will be adjusted based on the dosing interval (eg, use Date of last bimekizumab dose in the Initial Treatment Period – Date of first dose in the Initial Period + 28 days).

Note: If date of last dose in the Initial Treatment Period + 14 days (or + 28 days in the case of Q4W dosing) extends to a date beyond the date of first dose in the Maintenance Treatment Period, then this calculation reverts to:

- Date of first dose in the Maintenance Treatment Period – Date of first dose in the Initial Treatment Period + 1.
- For participants who die during the Initial Period, if date of last dose in the Initial Period + 14 days (or date of last bimekizumab dose in the Initial Treatment Period + 28 days in the case of Q4W dosing) extends to a date beyond the date of death, then this calculation reverts to:
 - Date of death – Date of first dose in the Initial Period + 1.

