2.3.2.2 Initial Treatment Period (Weeks 0-16) and Maintenance Treatment Period (Weeks 16-48)

Eligible study participants will be randomized in a 2:2:2:1 ratio as noted in the Study Schema to:

- Bimekizumab 320mg Q2W from Weeks 0 to 48
- Bimekizumab 320mg Q4W from Weeks 0 to 48
- Bimekizumab 320mg Q2W to Week 16, continuing on 320mg Q4W from Weeks 16 to 48
- Placebo to Week 16, continuing on bimekizumab 320mg Q2W from Weeks 16 to 48

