7 MEASUREMENTS OF TREATMENT COMPLIANCE

Due to the method of administration of the treatments, compliance will be examined in terms of completed injections.

Treatment compliance will be calculated as:

$$\frac{N_{actual}}{N_{expected}} \times 100\%$$

where N_{actual} is the total number of actual (completed) injections, and $N_{expected}$ is the total number of expected injections. In this study, dosing occurs every 2 weeks from Week 0 to Week 46, where 2 injections are administered at each given visit either with active dosing or placebo injection. It is expected that a participant should complete a total of 48 injections by the end of study. If a participant discontinues early, then the number of expected injections is based on the time of early discontinuation relative to the dosing visits. For example, if a participant discontinues after Week 8 visit and prior to Week 10 visit, the total number of expected injections will be 10.

A summary of percent treatment compliance categorized as <75% and $\geq 75\%$ will be provided by treatment group for each study period (Initial Treatment Period for the RS, Maintenance Treatment Period for the MS, and the combined Initial and Maintenance Treatment Period for the AMS).

A by-participant listing of treatment compliance will be provided.

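### For Q4W, the duration cap tests an unqualified last dose instead of the last bimekizumab dose, and the Maintenance death rule lacks the condition that the Initial Period rule has

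*SAP*

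**What the plan says.** **Base rule.** In SAP 10.1.1.1, duration is last dose minus first dose plus 14 days. For Q4W the instruction is to "use Date of last bimekizumab dose in the Initial Treatment Period" and add 28 days. Section 10.1.2.1 has the same construction for Maintenance.

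**Cap.** The next note in 10.1.1.1 reads "If date of last dose in the Initial Treatment Period + 14 days (or + 28 days in the case of Q4W dosing) extends" past the first Maintenance dose. In that case duration becomes first Maintenance dose minus first dose plus 1. Section 10.1.2.1 repeats the test against the final Maintenance visit. Section 10.1.3.1 uses the Initial Period test to decide whether 1 day is subtracted from the sum of the two periods. None of the three notes restricts the last dose to bimekizumab.

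**Death.** The Initial Period rule applies only if the dosing interval runs past the day the participant died. For Q4W its test is anchored on bimekizumab: "or date of last bimekizumab dose in the Initial Treatment Period + 28 days in the case of Q4W dosing) extends to a date beyond the". The Maintenance rule has no such condition: "For participants who die during the Maintenance Treatment Period, then this calculation reverts to". The value it then assigns is death minus first Maintenance dose plus 1.

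**Injection schedule.** Section 7 says that "dosing occurs every 2 weeks from Week 0 to Week 46". On what is given at those visits, it adds: "where 2 injections are administered at each given visit either with active dosing or placebo injection". Section 2.3.2.2 lists the regimen as "Bimekizumab 320mg Q4W from Weeks 0 to 48".

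**The concern.** Within 10.1.1.1 the same quantity has two anchors for Q4W. The base rule and the death rule use the last bimekizumab dose; the cap between them uses the last dose without qualification. Because Q4W participants also have injections at the in-between visits, their last injection in each period is normally a placebo given 2 weeks after the last active dose. Adding 28 days to that date overshoots the period end, so the cap fires and overrides the bimekizumab-based figure. A cap that should only shorten duration then lengthens it, and only in Q4W periods, so the two regimens are measured by different rules.

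The Maintenance death rule is a separate matter with the same direction of error: without the condition, time after treatment has stopped is counted as study medication duration.

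At stake is the extent of exposure by regimen in 10.1, including the cumulative-duration categories.

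**Working it through.** **Inputs.** Visits every 2 weeks, Weeks 0 to 46, 2 injections each (Section 7). Initial Period 112 days (10.1.1.2). Base, cap and death rules from 10.1.1.1, 10.1.2.1 and 10.1.3.1. Assumptions: Q4W active doses at Weeks 0, 4, 8, 12, then 16 to 44 in 4-week steps (the SAP does not list the active weeks), and visits on nominal days.

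**Reproducing the SAP's figures.** 24 visits × 2 = 48 injections, and 5 visits to Week 8 × 2 = 10, both as in Section 7. Q4W base rule with full adherence: Week 12 is day 84, and 84 + 28 = 112 days, the stated period length.

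**Initial Period, Q4W, participant enters Maintenance.** With the Week 14 placebo given, the literal test is 98 + 28 = 126 > 112, so the cap fires and assigns 112 + 1 = 113.

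| Case | Base rule | Literal cap | Cap on last bimekizumab dose |
|---|---|---|---|
| Full adherence | 84 + 28 = 112 | 113 | 112 |
| Week 12 missed, Week 14 placebo given | 56 + 28 = 84 | 113 | 84 |
| Weeks 8 and 12 missed, Week 14 placebo given | 28 + 28 = 56 | 113 | 56 |
| Weeks 12 and 14 both missed | 84 | 70 + 28 = 98, no cap: 84 | 84 |

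The ±3-day visit window does not alter the trigger: at worst 95 + 28 = 123 against 115.

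**Maintenance, Q4W.** Week 44 missed and Week 46 placebo given: base rule (40 − 16) × 7 + 28 = 196. Literal test: 46 × 7 + 28 = 350 > 336, so 224 + 1 = 225. Full adherence: 224 by the base rule, 225 literal. If Weeks 44 and 46 are both missed, 42 × 7 + 28 = 322 ≤ 336 and 196 stands.

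**Q2W comparison.** Week 46 missed: (44 − 16) × 7 + 14 = 210. The interval ends at Week 46, the cap does not fire, and the missed interval is lost.

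**Categories.** 84 days is 12 weeks; 113 days passes 16 weeks. For the combined period with only Week 44 missed, the base rules give 112 + 196 = 308 days (44 weeks, so the 40-week category). The literal rules give 113 + 225 − 1 = 337 days, which passes 48 weeks.

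**Maintenance death rule.** Last Q2W dose Week 18, death Week 40: the rule gives (40 − 16) × 7 + 1 = 169. With the Initial Period's condition the result would be (18 − 16) × 7 + 14 = 28. With last dose at Week 20 it is 169 against 42 (Q2W) or 56 (Q4W). The Initial Period rule does not behave this way: last Q2W dose Week 4, death Week 14 gives 28 + 14 = 42.

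**The case against.** **The parenthesis is ambiguous.** The cap note does not mention placebo and directly follows the sentence that defines the Q4W calculation from the last bimekizumab dose. It can be read as capping that quantity, which gives 84 days and no error. This stands as a possible reading. The literal one is still the more natural, because the death rule in the same section spells out bimekizumab and the cap does not. The Amendment 1 log (Section 13.1) also shows the bimekizumab wording being struck from the cap notes in 10.1.1.1 and 10.1.2.1. That log is no error in itself, but it makes the literal reading harder to dismiss.

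**The 84 days is a convention.** The last-minus-first formula ignores gaps inside a period: a Q4W participant who misses Week 8 but takes Week 12 keeps 112 days. This is correct. The comparison is with the SAP's own base rule, not with true exposure. Missed injections also remain visible in the Section 7 compliance summary and listing.

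**The death case is unusual.** The Safety Follow-up visit falls 20 weeks after the last dose, so Week 38 after a Week 18 dose. The example therefore needs someone who stopped drug but kept attending Maintenance visits. Section 4.2.1.4 (treatment policy strategy) provides for such participants. The sentence may simply have lost its conditional clause, but as printed it has none.

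**Stronger inferences to avoid.** A reader might infer that 28 days are added to a placebo injection in the reported duration, that every Q4W duration is materially inflated, or that safety rates are biased. The 28 days is only the trigger; the value assigned is period length plus 1. A fully adherent participant differs by 1 day. The exposure-adjusted rates in 10.2.1 use time at risk, which is defined separately.

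**Conclusion.** The wording is inconsistent and, run literally, gives wrong durations in specific cases. The cap effect needs a missed last active dose, a later placebo injection in the same period and, for the Initial Period, entry into Maintenance. When these coincide the overstatement is 29 days: 113 against 84 (29/84, about 35%) or 225 against 196 (29/196, about 15%). The death rule overstates duration only when death falls within Maintenance and later than the dosing interval after the last dose.

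These are sizes for single constructed participants, not effects on group exposure. The SAP gives no figure for how many would qualify; few are likely, but the error always runs towards more exposure. It rests on active Q4W doses every 4 weeks from Week 0 and on the literal reading of the cap. Only descriptive study medication duration, its combined-period sum and the cumulative-exposure categories can change. Exposure-adjusted incidence and event rates and all efficacy results are unaffected. This is a minor correction, worth making because the two readings give different numbers.

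**What to change.** In the cap notes of 10.1.1.1, 10.1.2.1 and 10.1.3.1, state that for Q4W the 28 days are counted from the date of the last bimekizumab dose in the period, using the construction already in the Initial Period death rule. Change all three together; otherwise the 1-day subtraction in 10.1.3.1 would be applied when the cap in 10.1.1.1 had not fired.

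In 10.1.2.1, apply the death rule only if the last dose plus 14 days (last bimekizumab dose plus 28 days for Q4W) runs past the date of death, as in 10.1.1.1.

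The cost is a few words in three notes, one added condition and a small programming change. No new data are needed. Reported Q4W exposure may fall slightly.
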